14.1.3. Methodology of data analysis

14.1.3.1. Statistical methods

It is assumed that of the primary variable, being a dichotomous qualitative, there is not enough data available regarding its distribution and, therefore, non-parametric statistical techniques will be carried out.

14.1.3.1.1. UNIVARIATE STATISTICS

In order to prove the veracity of the following null hypothesis, in the previously calculated sample it will be necessary to use a univariate nonparametric test for related samples; Mc Nemar test.

H0: Successful antebrachial venipuncture at the first attempt is not affected by the use of alternative methods.

H1: Successful antebrachial venipuncture at the first attempt if it is affected by the use of alternative methods.

The alternative methods refer to the interventions mentioned above.

If Mc Nemar's test results in a p-value <0.05 , the null hypothesis can be rejected and the alternative approved. As a consequence, there will be a need to know which alternative method of the three tested is the most effective.

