14. STATISTICAL ANALYSIS PLAN

14.1. Main analysis

14.1. 1. Definition of variables

Primary variable

Successful venipuncture at the first attempt. Dichotomous qualitative variable. Success / Failure

Secondary variables

Successful venipuncture frequency. Discrete quantitative variable. (1,2,3,4)

Visual intensity of hemolysis. Discrete quantitative variable. It is measured in stadiums.

Scale of expressed pain intensity (VAS). Discrete quantitative variable.

Scale skin types Fitzpatrick. Discrete quantitative variable.

Ingestion of liquids (less than 500 ml) in the last 6-8h prior to cannulation. Discrete quantitative variable (measured in glasses); it will be transcribed continuously for statistical analysis.

Affiliation of individuals

Respected fasting of 6-8 hours. Dichotomous qualitative variable.

Age. Quantitative variable continues.

Sex. Dichotomous qualitative variable.

Race. Discrete quantitative variable. 1 -> Caucasian 2 -> Black 3 -> Asian 4 -> Latin

BP. Continuous quantitative variable.

HR. Continuous quantitative variable.

T. Continuous quantitative variable.

BMI Continuous quantitative variable.

14.1. 2. Sample size calculation

The sample calculation is performed with the GRANMO calculator (63). It assumes a random risk (alpha) of 5% and a statistical power (beta) of 80%; for which it is tried to prove the veracity of the null hypothesis, of bilateral type.

That is, the risk of rejecting the null hypothesis when this is true is 5%, and the probability of not rejecting it being false is 20%.

In the literature, the success of peripheral intravenous canals was recorded in the first attempt, using the usual technique, in 74% of the cases (55). Currently, a proportion of peripheral intravenous cannulation has been registered at the first attempt of 73%, in an ultrasound ecoguided manner (33). In relation to the second successful attempt, in the usual clinical practice it amounts to 92% of the cases and, in the ultrasound ecoguided to 91% (33.55).

For the present work we intend to achieve a 95% success rate in antebrachial venous cannulation at the first attempt. Thus, overcome with one of the alternative methods proposed in this study the cumulative proportion of the second attempt of the usual and eco guided clinical practice.

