It is considered a clinically relevant difference the successful venous cannulation at the first attempt when, not only allows the cannulation at the first attempt of those cases that hypothetically would be observed, but accumulate to those cases that, in a way observed in the literature, the cannulation has been achieved at the second attempt, and hypothetically, that success can be achieved in the first attempt.

The comparative indicators are based on the comparison method and the reduction of intraindividual variability. It is considered a root of the experience, one of them is lost; An average of both percentages has been made, thus obtaining a 12% loss approximately.

Therefore, the calculation of the sample size should be followed through the modality of proportions, paired measures (repeated in a group). Fix in the proportion with pre-intervention event 0.74, in the proportion with post-intervention event 0.95, and the loss ratio 0.12.

Finally, the estimated sample size is 60 subjects.

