14.1.3.1.2. MULTIVARIATE STATISTICS

Therefore, it is considered pertinent to perform a logistic regression, multivariate statistics. The primary variable is assumed as the dependent variable and the secondary variables as returnable or explanatory. The primary variable fulfills the requirement of being dichotomous and the return variables assume any type of variable. It is assumed the need to create dummy variables with alternative methods, whose reference will be the comparator.

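### The primary test averages over the three methods and the primary comparison between them is made to follow from its significance, so one effective method would usually fail the primary test

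*Combined protocol and SAP*

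**What the plan says.** The main objective (5.2.1) is to find which use of heat and/or pressure gives the best first-attempt success relative to usual practice. Section 10.2.1 counts effectiveness as reached when any one of the three interventions exceeds 74%. The design target in 14.1.2 is 95% at the first attempt, so as to "overcome with one of the alternative methods proposed in this study the cumulative proportion of the second attempt".

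The primary test in 14.1.3.1.1 has a single null hypothesis about the alternative methods taken together, tested by one McNemar test in the calculated sample. If p<0.05 the null is rejected, and the text continues: "As a consequence, there will be a need to know which alternative method of the three tested is the most effective". Section 14.1.3.1.2 then opens: "Therefore, it is considered pertinent to perform a logistic regression, multivariate statistics", with dummy variables for the methods and the comparator as reference. Nothing is said about what follows if p is 0.05 or more.

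Several other places address the methods with no stated condition: cumulative incidence of success and failure (14.1.3.2.1), an odds ratio for each intervention (14.1.3.2.2), and the criterion in 10.2.1. Section 14.3 assigns a logistic regression to the effectiveness of all methods, to be run together with the main multivariate analysis.

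**The concern.** A pooled McNemar test responds to the average difference over the three methods. The objective asks about the best of them. If one method does what the design hopes and the other two do nothing, the tested difference is a third of the target: (0.21 + 0 + 0)/3 = 0.07. The primary test is then likely to be non-significant, and the step meant to identify the best method has no stated trigger. The report could carry a non-significant primary test beside a per-method odds ratio or success rate pointing the other way, and the plan does not say which answers the main objective.

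**Working it through.** **Inputs.** Success 0.74 and 0.95, 12% loss: "Fix in the proportion with pre-intervention event 0.74, in the proportion with post-intervention event 0.95, and the loss ratio 0.12" (14.1.2). Two-sided alpha 5%, power 80% (14.1.2). Model: "the calculation of the sample size should be followed through the modality of proportions, paired measures (repeated in a group". Allocation is equal, 4 of every 12 envelopes per method, five blocks (6.3), so 20 per method. The abstract (2.13) gives 54 subjects and 14.1.2 gives 60. Since 60 × 0.88 = 52.8, 54 is read here as completers, 18 per method; the two statements should be reconciled. The within-pair correlation is not in the documents, so a range is shown.

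**The plan's own figure.** Let b and c be the probabilities of success only with the intervention and only with the comparator, d = b − c and pd = b + c. Independent responses give b = 0.95 × 0.26 = 0.247, c = 0.74 × 0.05 = 0.037, pd = 0.284, d = 0.21.

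n = [1.96·√pd + 0.8416·√(pd − d²)]² / d² = [1.96·√0.284 + 0.8416·√0.2399]² / 0.0441 = 48.1.

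Adding the continuity term 1/d = 4.8 gives 52.9, and 52.9/0.88 = 60.1, which matches the stated 60. The figure therefore rests on one paired group in which every subject's success probability rises from 0.74 to 0.95, that is, on all three methods working.

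**One method at 95%, two at 74%.** For a null method with independent responses, b = c = 0.74 × 0.26 = 0.1924. Averaging over methods: b = (0.247 + 2 × 0.1924)/3 = 0.2106, c = (0.037 + 2 × 0.1924)/3 = 0.1406, pd = 0.3512, d = 0.07.

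Power = Φ{[√54·d − 1.96·√pd] / √(pd − d²)} = Φ{(0.514 − 1.161)/0.588} = Φ(−1.10) ≈ 0.136.

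**Simulation** (200,000 trials per setting, 18 pairs per method, within-subject correlation 0, 0.2 and 0.35):

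| Methods at 95% (others 74%) | Pooled test p<0.05, exact | Asymptotic |
|---|---|---|
| One | 9–11% | 14–16% |
| Two | 36–49% | 45–59% |
| Three | 82–97% | 88% at correlation 0, higher above |

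At the limit where no subject succeeds only with the comparator, the one-method case gives 16% (exact) or 54% (asymptotic). With independent responses, 80% power for d = 0.07 would need [1.96·√0.3512 + 0.8416·√0.3463]²/0.0049 ≈ 560 pairs.

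**Detecting a given effective method in its own 18 pairs.** The plan specifies no per-method McNemar test, so this is an illustration (exact test):

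| Methods that work | Pooled p<0.05 and own unadjusted p<0.05 | No condition, Holm-adjusted |
|---|---|---|
| One | about 4% | 7–8% |
| Two | 11–13% | 7–8% |
| Three | 16–17% | 6–8% |

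**The case against.** A reader might infer that the methods are examined only if the pooled test is significant, or that a non-significant result stops the analysis. The documents do not support that. The cumulative incidence, the odds ratios and the criterion in 10.2.1 are unconditional as written. The regression in 14.3 is linked to the main one in timing, with no explicit condition. The plan states no conclusion for p of 0.05 or more. A good method would still be estimated.

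The one-method pattern is also not the only plausible one. The third arm combines heat and pressure, so if either works alone the combination may work too. The pooled test is then significant in 36–49% (exact). This stands, and it is still well short of 80%. A case in which one method harms and cancels another has no basis in the documents and is not relied on.

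Nor is the condition the main limit on power: 18 pairs per method is. Unadjusted, unconditional exact tests would find a single effective method in 16–17% of trials, but the fair comparison is with the adjusted contrasts proposed here, at 7–8%. When two or three methods work, those contrasts detect a given method less often than unadjusted tests after the pooled test. The two procedures do not control the same error, but the cost is real.

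Finally, the pooling is read from the single null hypothesis and the reference to the whole calculated sample; the text does not use the word. No other reading fits, since no per-method McNemar test is planned.

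**Conclusion.** The point holds for the primary inference. The primary test answers whether the methods work on average, and the primary comparison between them is introduced as a consequence of its significance, while the objective, the criterion and the 95% target concern a single best method. If one method works as hoped and two do nothing, the primary test fails in about 84–91% of trials (100% minus 9–16%). The method would then appear only in estimates with no stated condition, and no rule says which result prevails. This rests on 54 completers split equally, the plan's 74% and 95%, and an assumed within-subject correlation of 0 to 0.35. The exception is the asymptotic test at the limit with no adverse discordance, where the pooled test is significant about half the time.

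**What to change.** In 14.1.3.1.1 and 14.1.3.1.2, remove the dependence of the method comparison on p<0.05. Keep the pooled McNemar test as an overall summary. State that the analysis of the main objective is the three paired method-versus-comparator differences in first-attempt success, each with a confidence interval and a Holm-adjusted p-value, reported whatever the pooled p-value. Say whether McNemar is exact or asymptotic, since the results differ materially at 18 pairs. State that the odds ratios, cumulative incidences and the criterion in 10.2.1 are supportive.

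The cost is SAP wording, with no new subjects or data. The downside is the lower adjusted detection shown above when two or three methods work. It does not make the sample sufficient: by the same uncorrected formula with independent responses, 80% power per method needs 49 pairs each (147 completers) at 0.05, or 65 each (195 completers) at 0.05/3. The per-method results should therefore be read mainly as estimates with their intervals.

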2.13. Subjects and sample size

Population. Adult healthy subjects.

Sample size. It is required to enroll 54 subjects with a 95% of level of confidence and 80% level of power.

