4.2. Justification

This study, which precedes the present one, concludes that: the application of this intervention is effective for the exacerbation of antebrachial venous perception, it denotes a characteristic of protection against the consequences that a difficult venous perception entails, thus reflecting a high impact avoidable potential of difficult venous perceptions, and all that this entails. Finally, it reveals that it is possible to benefit from this intervention to the entire population, but it is more fruitful if it is intended for subjects with a compromised venous perception, or with a low stage according to the VIA scale (10,36).

Likewise, the study ends with the need to which it is intended to respond in this protocol: clarify the cause of the finding found; that is, if the increase in antebrachial venous perception is due to exposure to dry heat and / or high stagnation pressure (37).

In the same way, it has been considered that the evaluation of the quality of the blood samples could be justified, in what refers to the intensity of hemolysis. No study has been found that proves, empirically and validly, what both Lundbeg et al. like other authors in the pre-pre-analytical phase; number of attempts in intravenous cannulation, pain and tourniquet aspects with respect to the intensity of hemolysis (25, 26, 28,30).

As a consequence, it has also been considered that the need to design and validate a visual scale of hemolysis could be justified; Detecting the intensity of hemolysis in a precise and valid way.

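### The plan aims to name the most effective of three interventions but prespecifies no contrast between them, no multiplicity control and no rule for making the claim

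*Combined protocol and SAP*

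**What the plan says.** The main objective in 2.11 is to identify the most effective of dry heat, high tourniquet pressure and their combination, compared with current practice. Section 5.2.1 says much the same, again relative to usual practice.

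Section 14.1.3.1.1 tests the alternative methods with a McNemar test. If p < 0.05, "there will be a need to know which alternative method of the three tested is the most effective". Section 14.1.3.1.2 responds with a logistic regression: "It is assumed the need to create dummy variables with alternative methods, whose reference will be the comparator". Section 14.1.3.2.2 adds an odds ratio for each intervention. Section 14.3 sends the secondary objective on the effectiveness of all methods to the same regression.

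The effectiveness criterion (2.15, 10.2.1) is met when any one intervention exceeds the 74% taken for usual practice.

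Under 6.2 each subject receives one intervention and the comparator. Under 6.3 the envelopes are split 4:4:4 in each block of twelve, over five blocks.

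**The concern.** A coefficient against the comparator shows whether a method beats usual practice. It does not show whether that method beats another one. The plan asks the second question and prespecifies only the first kind of term. It has no test that the three interventions are equal, no pairwise contrast, no adjustment for three comparisons and no provision for an unresolved ranking.

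An analyst who follows the text has estimates to rank and no criterion for when a ranking is supported. The conclusion at stake is the one in the main objective. The tests of each method against the comparator are not affected by this point.

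**Working it through.** **Inputs from the documents.** Two-sided alpha 5%, power 80%, rates 0.74 and 0.95, losses 12% (14.1.2). Sixty subjects in a 4:4:4 allocation (6.3). The abstract (2.13) gives 54, read here as completers.

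**The plan's own figure.** "Fix in the proportion with pre-intervention event 0.74, in the proportion with post-intervention event 0.95, and the loss ratio 0.12" leads to "Finally, the estimated sample size is 60 subjects". The documents give no discordance, so I assume independent responses within a subject:
- Discordant proportion: 0.74 × 0.05 + 0.26 × 0.95 = 0.284. Difference d = 0.21.
- McNemar: n = (1.960 × √0.284 + 0.842 × √(0.284 − 0.21²))² / 0.21² = 48.1 pairs.
- Continuity correction: (n/4) × (1 + √(1 + 2/(n × d)))² = 52.8 pairs. Then 52.8/0.88 = 60.0.

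The 60 is therefore reproduced, and it is the size for one paired comparison with the comparator. No comparison between interventions entered it.

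**Subjects per intervention.** 5 × 4 = 20 randomised, or 54/3 = 18 if 54 complete evenly.

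**How often a leader appears.** The documents give no rate for each intervention, so the rates below are assumptions shown as a range. I treated the three success counts as independent binomials with n = 18 and enumerated all outcomes. The last column is 1 − Π(1 − pᵢ¹⁸).

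| True rates | Any sole leader | True best leads alone | Another leads alone | At least one arm 18/18 |
|---|---|---|---|---|
| 0.95, 0.95, 0.95 | 49% | none is best | – | 78% |
| 0.90, 0.90, 0.90 | 66% | none is best | – | 39% |
| 0.85, 0.85, 0.85 | 72% | none is best | – | 15% |
| 0.95, 0.90, 0.90 | 65% | 41% | 24% | 56% |
| 0.95, 0.85, 0.85 | 77% | 63% | 14% | 46% |
| 0.95, 0.74, 0.74 | 93% | 91% | 3% | 40% |

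The remainder in each row are ties for the top. With 20 per arm the picture is similar: 52%, 68% and 74% for the three equal cases.

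**Precision of one contrast, 18 per arm.** The half-width is 1.96 × √(p₁(1 − p₁)/18 + p₂(1 − p₂)/18).
- 0.95 v 0.90: 1.96 × √(0.0475/18 + 0.09/18) = 0.17.
- 0.95 v 0.85: 1.96 × √(0.0475/18 + 0.1275/18) = 0.19.

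By Fisher's exact test, 18/18 differs at p < 0.05 only from 13/18 or fewer, a gap of 5/18 = 28 points.

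**Power of one contrast at two-sided 0.05.** For the plan's own gap, 0.74 v 0.95, the pooled rate is 0.845.
- Power with 18 per arm: Φ[(0.21 × √18 − 1.960 × √(2 × 0.845 × 0.155)) / √(0.74 × 0.26 + 0.95 × 0.05)] = Φ(−0.23) = 41%. With 20 per arm it is 45%. Fisher's test gives 27% and 33%.
- Size for 80% power by the matching formula: 46 per arm for 0.74 v 0.95, and 141 per arm for 0.85 v 0.95, before losses and before any multiplicity adjustment.

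**The case against.** **The objective and the effectiveness criterion are set against usual practice, so comparator-reference terms are the right ones.** This stands in part. Those terms answer whether each method works. They do not answer which of the three is most effective, which 14.1.3.1.1 asks in so many words.

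**The model already contains the contrasts.** This is correct. A reader might infer that the comparator-reference coding prevents comparison of the interventions. It does not, because each contrast is a difference of two fitted coefficients. The fault is one of prespecification.

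**No text says that the largest coefficient wins.** Also correct. A reader might infer that rule, but the documents state no rule at all, and that is the gap.

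**Chance leadership depends on the scenario.** It does. If one method reaches 0.95 and the others stay at 0.74, the true best leads alone in 91% of trials. It would be too strong to say that any method named best would be named by chance. Raw counts also simplify the planned covariate-adjusted regression.

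**The four conditions form a heat-by-pressure 2 × 2, so the plan wastes information.** A reader might infer a free gain. If heat and pressure effects add with no interaction, the variance of each effect falls to two thirds. Once the interaction is fitted, the coding is equivalent to the three dummies and the gain disappears. Additivity on the risk scale also fails at the design effect: 0.74 + 0.21 + 0.21 = 1.16. Section 4.2 does raise heat versus pressure, but about venous perception rather than first-attempt success.

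**Conclusion.** The point holds as a gap in prespecification. The stated main conclusion, which method is most effective, has no planned contrast, no multiplicity control and no claim rule behind it.

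The risk of an unsupported ranking is material when the methods are equal or close, and small only when one method is far ahead. Even then, leading is not the same as being shown superior: at 0.95 v 0.74 a single unadjusted contrast has about 41% power with 18 per arm.

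These figures rest on assumed rates for each intervention, on independent arms of 18, and on raw success counts. The absence of the contrasts and of the rule rests on the text alone.

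**What to change.** In 14.1.3.1.2:

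- Prespecify three contrasts, combination minus heat, combination minus pressure, and heat minus pressure, with Holm-adjusted p values and confidence intervals.
- Use a method that respects the two observations per subject and still works when an arm has 100% success. Penalised or exact methods, or risk differences with score-type intervals, would serve. Ordinary logistic contrasts would be infinite whenever a compared arm is 18/18, and at least one arm is in 40% to 78% of trials in the scenarios above where the best rate is 0.95.
- State the claim rule: a method is called most effective only if its contrasts with both of the others exclude no difference. Otherwise report each method against the comparator and label the ranking descriptive and unresolved.
- Heat, pressure and heat × pressure terms may be reported as a description, with no claim of added precision.

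The cost is SAP wording and a different fitting method; no new data, subjects or procedures are needed. The downside is that at this size the answer will often be that the ranking is not resolved.

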14.1.3.1.2. MULTIVARIATE STATISTICS

Therefore, it is considered pertinent to perform a logistic regression, multivariate statistics. The primary variable is assumed as the dependent variable and the secondary variables as returnable or explanatory. The primary variable fulfills the requirement of being dichotomous and the return variables assume any type of variable. It is assumed the need to create dummy variables with alternative methods, whose reference will be the comparator.

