8.3. Description of the comparator

Usual practice, up to now: The steps established in the standardized and approved venipuncture guide CLSI GP41-A6 (44) have been followed. It has been taken into account, the modification of said guide by Lima-Oliveira et al. in the order of steps to follow to put on the gloves; in such a way that it adapts to the usual clinical practice in Spain (27).

Therefore, the steps of the latter, CLSI GP41-A6 (44), will be followed, allowing the gloves to be placed in the order considered by the nurses. The irrevocable condition will be to comply with this step, as well as to comply before the step corresponding to the venipuncture itself.

The usual method does not involve the application of topical heat previously, and the tourniquet corresponds to latex.

In this protocol, venipuncture will refer to the insertion of peripheral intravenous catheter, from the caudal to the cranial part of the forearm. It will be considered successful, after the insertion of the catheter, venous reflux occurs and the extraction of a basal blood sample is possible.

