9.4. Development of fieldwork of the trial

The first evaluation of the VIA scale (36) will be carried out, according to the number of optimal puncture points (PPO), before the application of the arm assigned by the main researcher and will correspond to the inclusion and exclusion criteria; pre-intervention assessment. This will be transcribed as the first VIA scale assessment (36).

In the interventions, the VIA scale will be evaluated twice (36). The second assessment will be carried out after the application of the intervention or randomly assigned comparator; and before performing venipuncture.

In the case of the comparator, it will only be evaluated once; It will not be assessed if it denotes a change of stage, since no intervention is applied. If this corresponds to the first period, the registration stage of the inclusion / exclusion criteria will be transcribed, if it corresponds to the second period, the corresponding nurse will assess it.

In both cases, the intervention or comparator will be applied, the success or failure in successful venipuncture will be recorded on the first attempt. In the case of failure, the attempt number to which the catheterization was possible will be recorded. Table 2

| ORGANIZATION CHART ACCORDING TO VISITS | | |
|---|-----------------|---|
| ENROLLMENT VISIT | FIRST DAY ENTRY | SECOND DAY ENTRY |
| 
 1. Information Sheet 2. Informed consent form. 3. Training for the nurses listed on the form. | X | 
 1. Subjects inclusión according to inclusión and exclusión criteria VIA assessment 2. Randomized assignment 3. Intervention/comparator assigned application. 4. Post intervention VIA assessment. 5. VAS pain assessment. 6. FITZPATRICK scale skin assessment 7. Hemolysis analysis. |

Table 2. Organization chart according to visits. Own elaboration.

This organization chart, Table 2, will be specific to the first period of the clinical trial. Another detailed organization chart has been prepared for the two study periods in section 9.7.3.

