9.7. CLINICAL FINDINGS AND MATERIAL RESOURCES INVOLVED

9.7.1. Pain assessment

The evaluation of the pain will be carried out through the scale validated Visual Analog Scale (VAS) / numerical (45). Linear scale from zero to ten, from minimum pain to maximum perceived pain, escalating with integers in increasing order. The use of this scale is considered pertinent because it has been validated for the detection of both chronic and acute pain; through changes in temperature and for groups of individuals (45,46).

The individual will be provided with this scale, in paper format, so that he self-expresses the pain perceived in the venous cannulation with the randomly assigned method. It is provided immediately after the fixation of the vein catheter.

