14.3. Secondary analysis attached

It has been considered that the approach of non-main secondary objectives could be carried out through the following methodology:

To identify the effectiveness of all the methods used in antebrachial venipuncture, in what refers to venipuncture at the first attempt.

It is intended to be addressed by means of a logistic regression, at the same time as the multivariate statistics for the main variable.

To evaluate the intensity of hemolysis of the blood samples, in what refers to the applied method, respectively.

It is considered that there is enough information on this subject to use a parametric test. In this case, the intensity of hemolysis is the dependent variable, it is considered justified to use an ANOVA test of a block test.

Identify the frequency of successful venipuncture at the first attempt and analyze if there is an association between it and the demographic characteristics of the individuals.

It is intended to be addressed through descriptive statistics. To analyze the association, a logistic regression will be performed; multivariate technique.

Analyze the correlation between methods used, intensity of hemolysis and pain.

It could be considered that enough information is known about pain to use parametric techniques, it is supposed to be the dependent variable and it is discrete. Therefore, it is intended to be approached using the ANOVA statistical technique or two-way F-test without interaction.

Identify and quantify adverse events, as well as their relation to skin types.

For the identification and quantification, a descriptive statistic will be carried out. In order to assess the possible association, using the Fitzpatrick scale, it is considered that there is not enough information about its distribution, so it is considered appropriate to use a nonparametric type test; the Kruskal-Wallis test.

14.4. Intermediate analysis.

Does not apply.

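### The regression meant to pick the best of the three methods takes as predictors the attempt number, which defines the outcome, and pain and haemolysis, which are measured after it

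*Combined protocol and SAP*

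**What the plan says.** The main objective (Section 5.2.1) is to find which of heat, high pressure or both works best for first-attempt success. Section 14.1.3.1.1 tests the methods with McNemar and says that, if the result is significant, "there will be a need to know which alternative method of the three tested is the most effective". Section 14.1.3.1.2 answers with a logistic regression: "The primary variable is assumed as the dependent variable and the secondary variables as returnable or explanatory". Method enters as dummy variables against the comparator. There is no exclusion or selection rule.

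Section 14.1.1 lists five items as secondary variables:

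- "Successful venipuncture frequency. Discrete quantitative variable. (1,2,3,4"
- visual haemolysis
- VAS pain
- Fitzpatrick skin type
- fluid intake

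Age, sex, BMI and similar items stand under a separate heading. Section 14.3 uses the same model for the first secondary objective: "It is intended to be addressed by means of a logistic regression, at the same time as the multivariate statistics for the main variable".

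On timing, Section 9.4 says that after a failed first attempt "the attempt number to which the catheterization was possible will be recorded". Of the pain scale, Section 9.7.1 says "It is provided immediately after the fixation of the vein catheter". Section 8.3 counts a cannulation as successful when "venous reflux occurs and the extraction of a basal blood sample is possible", so the basal sample comes after it.

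**The concern.** A regression can compare the methods only if its other predictors are not the outcome itself and not consequences of the method. Three of the five listed variables fail that test. The attempt number, if that is what the 1-4 count is, contains the outcome. Pain and haemolysis are recorded after the outcome is known, and Section 14.3 itself treats both as responses; for haemolysis it says "In this case, the intensity of hemolysis is the dependent variable".

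This is the only inferential model the plan names for choosing between the methods. If it cannot be fitted as written, the predictors will be chosen during the analysis of a trial in which the investigator knows the allocation (Section 6.4). The obvious repair, dropping only the attempt number, leaves an answer adjusted for post-cannulation measures and possibly lacking some of the failures.

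**Working it through.** **Inputs.** Success 74% under usual practice and 95% as target; 92% cumulative success by the second attempt under usual practice; 12% losses (Section 14.1.2). Envelopes are split equally over the three methods (Section 6.3). The abstract's 54 subjects give 18 per method and 108 records; 60 subjects give 20 per method. Rates for the two methods that do not reach 95% are not in the plan and are assumed.

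**The plan's own figure.** The McNemar sample size with maximum discordance 0.26 + 0.05 = 0.31 and difference 0.21 is (1.96√0.31 + 0.8416√(0.31 − 0.21²))² / 0.21² = 52.75, so 53. Then 53/0.88 = 60.2. The stated 60 is reproduced, so these rates are the right basis.

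**1. Is the count the attempt number?** Each subject has two periods (Section 6.2), so a count of successes could not reach 4. Section 9.4 records an attempt number, and no other attempt count is defined. The reading is an inference, but it fits.

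**2. Separation.** Let K be the attempt number, with success meaning K = 1. Put b(1.5 − K) in the linear predictor. Every success scores +0.5b and every failure −0.5b or lower. The likelihood rises to 1 as b grows, so there is no finite maximum and the method odds ratios are not identified. In simulated trials (54 subjects, 18 per method, 95% against 74%), separation was complete in 2,000 of 2,000. A forced fit to pooled data gave log-odds standard errors of about 500 to 2,400. If K is entered only on failure, as Section 9.4 literally says, a complete-case fit keeps only failures and cannot be run either.

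**3. Pain and haemolysis.** Both follow cannulation (Sections 8.3, 9.2, 9.7.1, 10.2.3). Section 4.1.2 says repeated attempts can cause haemolysis. Section 9.8 says paraesthesia, a possible effect of cuff pressure, might lower pain. Adjusting for them therefore does not give the total method effect. The documents do not allow the bias to be sized. As an illustration, assume mean pain 3, SD 1.5, and 0.65 to 1.95 points more after a first-attempt failure. The true odds ratio is (0.95/0.05)/(0.74/0.26) = 6.68.

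| Assumed direct effect of method on pain | Odds ratio after adjusting for pain |
|---|---|
| none | about 6.7 |
| −1 point | 2.9 to 5.1 |
| +1 point | 8.9 to 15.4 |

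**4. Lost records.** Section 7.4 keeps a period-2 subject in whom cannulation was tried and never achieved. That record is a failure with no fixed catheter and no basal sample. At usual-practice rates, the share of first-attempt failures still uncannulated after attempt 2 is (1 − 0.92)/(1 − 0.74) = 0.308. So 0% (all cannulated later) to 31% of period-2 failures could drop out. Section 14.2.3.2 adds that the first samples cannot be scored visually, though absorbance and photographs will exist. No rule covers either case.

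**5. What remains after removing the three variables.** An arm with no failures still gives an infinite odds ratio. With 18 per method, the chance of no failures is 0.95¹⁸ = 0.397, 0.85¹⁸ = 0.054 or 0.74¹⁸ = 0.0044. The chance of at least one such arm, with one method at 95%, is:

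- other two at 74%: 1 − 0.603 × 0.9956² = 40%
- other two at 85%: 1 − 0.603 × 0.946² = 46%
- other two at 95%: 1 − 0.603³ = 78%
- 20 per method, other two at 74%: 36%

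With one method at 95% and two at 74%, expected failures are 54 × 0.26 + 18 × (0.05 + 0.26 + 0.26) = 24.3. That is 3.0 per slope for eight slopes (three methods, five secondary variables), or 4.1 for six (three methods, period, fluid intake, skin type).

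**6. Pairing (secondary).** The plan names no subject or period term. The log-odds standard error for an arm of 18 at 95% against 54 comparator records at 74% is √(1/(18 × 0.95 × 0.05) + 1/(54 × 0.74 × 0.26)) = 1.125 if pairs are ignored. It is 1.090 at within-subject correlation 0.2, and 1.056 at the maximum (0.74 − 0.74 × 0.95)/√(0.74 × 0.26 × 0.95 × 0.05) = 0.387. Ignoring pairs therefore overstates it by 3.2% to 6.5%. Between methods, with method terms only, the ratio is 1.00.

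**The case against.** The wording is loose, and method, the one predictor actually named, is not on the Section 14.1.1 list. Section 14.3 also suggests that the authors saw pain and haemolysis as outcomes. One could therefore call the predictor set ambiguous rather than wrong. Complete separation would also be obvious to any analyst, so a false winner by that route is unlikely. The McNemar test, the 74% criterion and the cumulative incidences do not depend on this model.

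Much of this is fair. The attempt-number reading is an inference, and no case of paraesthesia has been documented (Section 9.8), so a direct effect of method on pain is a possibility only. The zero-failure figures come from small arms, not from the wrong predictors, and support only the need for a fallback. Failures per slope describe how sparse the data are. The 31% is a ceiling: with the 24.3 failures split evenly over the periods it is about 12 × 0.31 = 3.7 of 108 records. The pairing effect is small and conservative.

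The objection does not rescue the text. The listed heading matches the regression's wording, and nothing removes an item. Noticing the separation leads naturally to dropping the count alone, and the timing of pain and haemolysis and their loss in never-cannulated failures rest on explicit statements.

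A further objection is that a Firth fallback ignores pairing. It still estimates the marginal odds ratio. In simulation its 95% intervals covered 94% to 96% of the time against the comparator and about 98% between methods.

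**Conclusion.** The model is wrong as written and must be corrected before analysis. With the attempt number among the predictors it yields no finite method odds ratio. That follows from the definition, given the attempt-number reading. With only that variable removed, the comparison is still adjusted for two post-cannulation measures and can lose 0% to 31% of period-2 failures at the plan's usual-practice rates. The size of the adjustment bias is unknown. With all three removed, at least one arm without failures remains likely (36% to 78%, depending on the assumed rates and arm size), so a fallback is needed. The McNemar test, the 74% criterion and the cumulative incidences stand. The odds ratio of Section 14.1.3.2.2 is unaffected provided it is computed from the crude counts, which that section does not state.

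**What to change.** In Sections 14.1.3.1.2 and 14.3, replace the reference to secondary variables as predictors with:

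> First-attempt success will be modelled on three method terms (reference: comparator) and period, with subject as the cluster (GEE, marginal odds ratios). Attempt number, VAS and haemolysis will not be predictors. Any covariates will be limited to variables already collected and fixed before cannulation (for example fluid intake and Fitzpatrick type), listed before analysis. If the model separates or any method has no failures, penalised (Firth) or exact estimation will be used. Odds ratios against the comparator and contrasts between the three methods will be reported with 95% CIs.

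Two details should be settled in that text. Name one fallback: Firth keeps the marginal odds ratio, whereas exact conditional regression estimates a conditional one. Say also that skin type qualifies as a stable trait, because Table 2 lists it after the pain score.

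The cost is wording in two sections and slightly more analysis work. No new data are needed.
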